- 3) Will use the Mass General Brigham Research Invitations procedures for recruitment. We will send prospective subjects a letter via the Research Invitation Program.

At the first point of contact (usually a phone call), a study co-investigator will provide a description of the study, discuss study procedure, and administer a phone screening questionnaire. Once the phone screening process is complete, the information gathered by the co-investigator will be taken to the PI of the study for further review. Once the PI agrees that the subject is thus far eligible, the subject will be scheduled their first visit. Consent form will be mailed to the subject ahead of time.

Informed consent will be obtained by a license physician, PI [name] [name] at SRH. The subject will meet with [name]. The test procedures will be described, and the testing equipment will be shown to the subject. [name] will clearly explain all the procedures and risks of the testing outlined in the consent form. The subject will be given an hour to consider their decision and will be encouraged to ask questions, both during the initial phone interview and throughout the study. [name] will answer any questions regarding the study at the time of the informed consent process. Once enrolled, the subject may pause or terminate his/her participation at any time during the study.

Participants will be randomized to receive active or sham RAVANS treatment 3 times per week for 2 weeks through a randomization approach with blocks of 4 (given the sample size of 48 participants, this would give 12 blocks of 4). Randomization of subjects will be blocked based on the 2 treatment options available.

V. STUDY PROCEDURES

First visit: consent, blood drawn, baseline evaluation, first RAVANS/Sham treatment

During this first visit, we will conduct the consent process. Participants that provide informed consent will be interviewed to complete inclusion/exclusion check list. The qualified subjects will be included in the study. They will complete the questionnaires (Demographic Data Questionnaire, Functional Comorbidity Index, Horowitz Lyme-MSIDS, Sedentary Behaviors Questionnaire, Fatigue Symptom Inventory, Brief Pain Inventory, Vulnerability questionnaire, Beck Depression Inventory, Beck Anxiety Inventory, Pittsburgh Sleep Quality Index), functional test (Timed Up and Go, 4 meter usually walking speed, NIH Toolbox cognitive battery), blood drawn and they will receive 1st RAVANS or sham treatment.

Blood test

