Subjects will receive RAVANS or sham treatment at clinic for 20 minutes. Subjects will complete the questionnaires (Horowitz Lyme-MSIDS, Sedentary Behaviors Questionnaire, Fatigue Symptom Inventory, Vulnerability Questionnaire, Brief Pain Inventory, Beck Depression Inventory, Beck Anxiety Inventory, Pittsburgh Sleep Quality Index), functional test (Timed Up and Go, 4 meter usually walking speed, NIH Toolbox cognitive battery), blood drawn for serum biomarkers (IL-6, IL-10, TNF, IL-1 β). Total visit times will be about 4 hours.

VI. BIOSTATISTICAL ANALYSIS

Our main outcome is to assess whether there is an improvement in symptoms (comparing before and after treatment) as indexed by HL-MSIDS score in the active RAVANS group as compared with sham. We chose the HL-MSIDS as the main outcome and therefore the other scale will be the secondary outcome. For the main analysis, we will compare the differences in HL-MSIDS changes between the two groups immediately after the end of treatment. We will therefore use an unpaired t-test for such analysis. Note here that we expect similar baseline level for both groups.

Besides this analysis, we will perform several exploratory analyses as listed below: we will compare the differences in changes in SBQ, FSI, BPI, BDI, BAI, PSQI, Timed- Up

and Go, 4m walk speed, NIHTB-CB, level of serum IL-6, IL-10, TNF, IL-1 β between the two groups immediately after the end of treatment. We will therefore use an unpaired t-test for such analysis.

Pearson correlation analysis will be applied to determine if serum level of biomarkers (IL-6, IL-10, TNF, IL-1 β) has correlation with symptom severity as index by HL-MSIDS, SBQ, FSI, BPI, BDI, BAI, PSQI, Timed- Up and Go, 4m walk speed, NIHTB-CB.

We will use the intention-to-treat analysis and do an analysis of only subjects that completed the 2-week study. For the intention-to-treat analysis, we will use a conservative method and assume that participants will not improve from the last measured point. The last-observation-carried-forward method will be appropriate because we expect no more than 10 percent of the observations were missing in each analysis.

Power analysis (e.g, sample size)

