Sample size was determined with reference to other studies that used similar endpoints. We assume that a standardized difference of 0.8 (the difference between groups divided by the standard deviation) is conservative to detect a clinically meaningful difference between groups (active RAVANS and sham). We will assume a type I error of 5% (alpha), a type 2 error of 10% (beta) and therefore the power will be 90%. Using the sample size calculation for a normal distributed population (t-test), 20 participants per arm will be necessary (total of 40 participants). Conservatively, we expect a 20% rate of dropout or loss to follow-up. We will assume that dropout participants will not improve from the last measured point; thus the sample size will be increased by 20% to 48 participants (24 per arm).

VII. RISK AND DISCOMFORTS

Blood Draws. Blood drawing may cause a small amount of pain. In addition, participants may get a temporary bruise or “black and blue mark”. Rarely, people faint when their blood is drawn. Very rarely, the vein may become red and swollen, or infected. If this occurs, we will treat the problem. Blood drawn will be performed by clinical phlebotomists to minimize the risk and discomforts.

Surveys/ Questionnaires. Some of the questions in the questionnaires may seem personal or embarrassing. Participants will be instructed that they may refuse to answer any of the questions that they do not wish to answer. If the questions make a participant very upset, we will help them to find a counselor. If participants develop fatigue during completing the questionnaire, we all ask the participant to take break.

RAVANS Risks: There is a small possibility of slight and temporary discomfort at the site where the electrodes are placed. Potential vaso-vagal reactions to stimulation

resulting in dizziness or light-headedness. The participant will be instructed to sit in chair while receiving RAVANS/Sham treatment.

The RAVANS procedure is without significant safety concerns. The electrical stimulator, checked by MGH Biomedical Engineering, has a current limiter preventing harmful stimulation levels.

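### At the stated 20% dropout, raising 40 to 48 does not deliver the allowance: about 38 participants complete, and counting dropouts as unimproved may leave the intention-to-treat analysis with less power than 20 completers per arm

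*Combined protocol and SAP*

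**What the plan says.** All the sizing text is in section VI (Biostatistical Analysis), under Power analysis.

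- Effect: "We assume that a standardized difference of 0.8 (the difference between groups divided by the standard deviation"). The plan does not say whether this is the effect among completers or among everyone randomised.
- Error rates: "We will assume a type I error of 5% (alpha), a type 2 error of 10% (beta"), from which it takes 90% power. It does not say whether the test is one- or two-sided.
- Base number: "20 participants per arm will be necessary (total of 40 participants").
- Dropout: "Conservatively, we expect a 20% rate of dropout or loss to follow-up".
- Allowance: after assuming that dropouts stay at their last measured point, "thus the sample size will be increased by 20% to 48 participants (24 per arm").

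Earlier in section VI the main outcome is the change in HL-MSIDS, compared by an unpaired t-test. Two analyses are planned: intention-to-treat, and completers of the 2 weeks only. For the intention-to-treat analysis, "we will use a conservative method and assume that participants will not improve from the last measured point". Last observation carried forward is justified there by an expectation that at most 10 percent of observations will be missing. The assessment table in section V schedules HL-MSIDS at Visit 1 and Visit 6 only.

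**The concern.** Two things in the allowance do not fit together.

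First, multiplying a required number by 1.2 does not preserve that number when 20% of those enrolled leave.

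Second, the increase is presented as following from the no-improvement rule, but that rule creates a different problem from lost numbers. It keeps dropouts in the intention-to-treat comparison with a change of zero, which pulls the two arm means together. Four more participants per arm offset a loss of numbers, but not necessarily a smaller difference.

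At stake is how a null result would be read. A reader would take 48 as already protected against 20% dropout in both planned analyses, and could over-interpret a non-significant result if it is not.

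**Working it through.** **Inputs from the plan:** 0.8 SD; 5% alpha; 20 per arm before and 24 per arm after the allowance; 20% dropout (Power analysis); at most 10% missing (section VI, analysis text); HL-MSIDS at Visits 1 and 6 only (section V table).

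**Assumptions not in the plan:** two-sided test (one-sided also shown); 0.8 SD is the completer effect; completer SD of 1 in each arm; equal dropout in both arms, all before Visit 6; sham mean change among completers from -0.4 to +1.0 SD, with improvement positive.

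**1. The plan's figure.** 40 × 1.2 = 48, so the stated number reproduces as a 20% increase.

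**2. What it leaves.** 48 × (1 - 0.20) = 38.4, or 19.2 per arm. Retaining 40 would need 40 / 0.80 = 50. Enrolling 48 retains 40 only up to 1 - 40/48 = 16.7% dropout. Two-sided t-test power at 0.8 SD is 69.3% with 20 per arm and 67.0% with 19.

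**3. Zero change for dropouts.** Someone who leaves before Visit 6 has only the Visit 1 score. Carrying it forward gives a change of exactly 0.

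With dropout fraction p and completer mean change m in an arm:

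- arm mean = (1 - p)m
- arm variance = (1 - p) + p(1 - p)m²

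At p = 0.2 the difference between arms is 0.8 × 0.8 = 0.64, and each arm's variance is 0.8 + 0.16m². For sham m = 0 and active m = 0.8:

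- variances 0.8 and 0.8 + 0.16 × 0.64 = 0.9024
- pooled SD = √0.8512 = 0.923
- standardized difference = 0.64 / 0.923 = 0.694

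**4. Intention-to-treat power, 24 per arm, two-sided 5%, noncentral t:**

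| Sham mean change (SD) | Std. difference, 20% dropout | Power, 20% | Std. difference, 10% missing | Power, 10% |
|---|---|---|---|---|
| -0.4 | 0.704 | 66.6% | 0.753 | 72.4% |
| 0 | 0.694 | 65.3% | 0.747 | 71.7% |
| +0.3 | 0.673 | 62.7% | 0.735 | 70.3% |
| +0.5 | 0.655 | 60.3% | 0.725 | 69.1% |
| +1.0 | 0.600 | 52.9% | 0.689 | 64.7% |

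Simulation with 200,000 trials per case agrees to within about one percentage point (for example 66.1% for sham change 0 at 20% dropout). If the SD is simply left at 1, power is 58.3% at 20% and 68.5% at 10%.

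**5. Comparison with 20 completers per arm (69.3%).** At 20% dropout every row is lower. At 10%, three rows are higher, one is about equal and one is lower. One-sided at 20% dropout, the range is 65.6% to 77.6% against 79.9% for 20 completers, so the ordering is the same.

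**6. The base number.** At 0.8 SD and 90% power, a two-sided t-test needs 34 per arm and a one-sided test 28. The stated 20 per arm gives about 69% two-sided, or 80% one-sided. The comparisons above therefore use 20 completers as the plan's own benchmark, not as an adequate number.

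**The case against.** The case for leaving the text alone has four parts.

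- **The completer shortfall is trivial.** This stands. It is 48 against 50 enrolled and about 2 points of power. The plan says only that it increases the number by 20%, which it does; it never promises 40 completers.
- **0.8 may already be the effect among all randomised.** The plan's definition is silent. On that reading nothing further is diluted and 24 per arm gives 77% two-sided. This stands as a possibility. The completer reading is the more natural one, because the plan sizes on 0.8 first and then treats dropout as a separate loss, but it remains an assumption.
- **The other stated rate removes the problem.** At 10% missing the shortfall largely goes away. This also stands, but the two rates conflict. With a single post-baseline HL-MSIDS, a participant lost before Visit 6 is a missing observation, so 20% dropout does not sit with at most 10% missing unless dropouts return for that visit. The trial was sized on 20%.
- **It is a pilot, and the base number is the larger error.** Both are true. Nevertheless the plan makes a formal power claim for a named main outcome, and correcting the base would repair neither the multiplication by 1.2 nor the dilution.

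A reader might infer that 24 enrolled per arm always gives less power than 20 completers. The documents do not support that: it needs both the 20% rate and the completer reading of 0.8.

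**Conclusion.** The concern holds in a conditional form. At 20% dropout, 48 enrolled leaves about 38 completers, a minor shortfall. If 0.8 SD is the completer effect and dropout is equal in the arms, intention-to-treat power at 24 per arm is about 53–67% (65% with sham change 0), below the 69% of 20 completers per arm. The loss against that benchmark is about 3 to 16 points. Its size depends on the sham change, which the documents do not give; its direction at 20% dropout does not, within the range tried. At 10% missing, power is about 65–72% and there is little or no loss over most of the range.

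It would be wrong to conclude that the allowance is what separates the trial from 90% power. Most of that gap comes from the base of 20 per arm, which gives about 69% two-sided before any dropout. The correction is worth making because it is cheap and concerns a figure on which the trial relies.

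**What to change.** Keep 48 enrolled, so the scheme in section IV ("through a randomization approach with blocks of 4 (given the sample size of 48 participants, this would give 12 blocks of 4") is unchanged, and revise section VI as follows:

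1. Reconcile the 20% dropout in the Power analysis with the 10% missing used to justify last observation carried forward.
2. State that 48 enrolled leaves about 38 completers (19 per arm) at 20% dropout.
3. State whether 0.8 SD applies to completers or to all randomised, and whether the test is one- or two-sided.
4. Replace the sentence that derives the 20% increase from the no-improvement rule with the actual two-sided power for 24 enrolled per arm: about 67% for the completer analysis; and, if 0.8 is the completer effect, about 53–67% for the intention-to-treat analysis at 20% dropout, with the assumed sham change shown. If the reconciled rate is 10%, give 65–72% for the latter.
5. Put these in place of the 90% figure, and do not describe 40 as the number that delivers 90% power.

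The cost is wording only: no extra participants and no change to randomisation or analysis. The downside is that the stated power becomes visibly less favourable.
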